4.0 PATIENT ELIGIBILITY

Important note: The eligibility criteria listed below are interpreted literally and cannot be waived. All clinical and laboratory data required for determining eligibility of a patient enrolled on this trial must be available in the patient's medical or research record which will serve as the source document for verification at the time of audit.

Laboratory Studies:

All laboratory studies to determine eligibility must be performed within 7 days prior to enrollment unless otherwise indicated.

Laboratory values used to assess eligibility must be no older than seven (7) days at the start of therapy. Laboratory tests need **not** be repeated if therapy starts **within** seven (7) days of obtaining labs to assess eligibility.

If a post-enrollment lab value is outside the limits of eligibility, or laboratory values are older than 7 days, then the following laboratory evaluations must be re-checked within 48 hours prior to initiating therapy: CBC with differential, bilirubin, ALT (SGPT), albumin and serum creatinine. If the recheck is outside the limits of eligibility, the patient may not receive protocol therapy and will be considered off protocol therapy.

Clinical Studies:

All clinical studies to determine eligibility must be performed within 7 days prior to enrollment unless otherwise indicated. Imaging studies must be obtained within 14 days prior to enrollment (repeat the tumor imaging if necessary).

Clarification in timing when counting days: As an example, please note that if the patient's last day of prior therapy is September 1st, and the protocol requires waiting at least 7 days for that type of prior therapy, then that patient cannot be enrolled until September 8th.

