4.2 Exclusion Criteria

4.2.1 Pregnancy or Breast-Feeding

Pregnant or breast-feeding women will not be entered on this study due to risks of fetal and teratogenic adverse events as seen in animal/human studies, OR because there is yet no available information regarding human fetal or teratogenic toxicities. Pregnancy tests must be obtained in girls who are post-menarchal. Males or females of reproductive potential may not participate unless they have agreed to use two effective methods of birth control, including a medically accepted barrier or contraceptive method (e.g., male or female condom) for the duration of the study and for 3 months + 2 days for males and 6 months + 2 days for females after receiving the last dose of BAY 1895344 (elimusertib) on the study. Abstinence is an acceptable method of birth control. Female patients must not breastfeed during treatment and until 4 months after last study drug administration.

4.2.2 Concomitant Medications:

4.2.2.1 Corticosteroids: Patients receiving corticosteroids who have not been on a stable or decreasing dose of corticosteroid for at least 7 days prior to enrollment are not eligible. If used to modify immune adverse events related to prior therapy, ≥ 14 days must have elapsed since last dose of corticosteroid (see [Section 4.1.7.1.d](#)).

4.2.2.2 Investigational Drugs: Patients who are currently receiving another investigational drug are not eligible.

4.2.2.3 Anti-cancer Agents: Patients who are currently receiving other anti-cancer agents are not eligible.

THIS PROTOCOL IS FOR RESEARCH PURPOSES ONLY, SEE PAGE 1 FOR USAGE POLICY

4.2.2.4 **Anti-GVHD agents post-transplant:** Patients who are receiving cyclosporine, tacrolimus or other agents to prevent graft-versus-host disease post bone marrow transplant are not eligible for this trial.

4.2.2.5 **CYP3A4 Agents:** Patients who are currently receiving drugs that are strong inducers or inhibitors of CYP3A4 are not eligible. Strong inducers or inhibitors of CYP3A4 should be avoided from 14 days prior to enrollment to the end of the study. Drugs that are considered sensitive or narrow therapeutic range CYP3A4 substrates should be avoided for the duration of protocol therapy. See [Appendix III](#) for a list of agents.

4.2.3 **Study Specific:**
Dedicated CNS imaging is not required but patients with current active CNS metastasis whether symptomatic or discovered incidentally without clinical symptoms, will be excluded from study participation.

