5.2 Criteria for Starting Subsequent Cycles

A cycle may be repeated every 28 days if the patient 1) has at least stable disease 2) all pre-cycle studies required per [Section 8.1](#) meet eligibility criteria-as defined in [Section 4.0](#) and 3) is otherwise eligible to continue agent administration per the requirements in [Section 6.0](#).

5.2.1 Recommendations for Starting Each Weekly 3-day Course:

BAY 1895344 (elimusertib) is administered on a 3-day on and 4-day off schedule, repeated 4 times each cycle. Hematologic toxicities are the most common toxicities with BAY 1895344 (elimusertib). Eligibility criteria require an ANC \geq 1000/ μ L and Platelets \geq 100,000/ μ L, hence these parameters also need to be met to start any cycle (See [section 4.1.11.1](#)). Once a cycle has started, patients are required to have an ANC $>$ 500/ μ L and Platelets $>$ 50,000/ μ L within 48 hours prior to initiation of each 3 day interval of BAY 1895344 (elimusertib) administration (i.e. ANC and platelet parameters must be met (without transfusion) within 48 hours of initiation of days 8, 15, and 21). If parameters are not met, this 3-day interval of BAY 1895344 (elimusertib) will be omitted and attempted to restart the following week (e.g. day 15 or 21). If more than one 3-day block of BAY 1895344 (elimusertib) is missed within a cycle (i.e. $<$ 75% of planned therapy is given for a particular cycle), that would be considered a hematologic DLT.

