- h. Electrolytes including serum creatinine, calcium (Ca⁺⁺), phosphorus (PO₄), magnesium (Mg⁺⁺)
- i. Creatinine Clearance or GFR
- j. Tumor disease evaluation: ^can occur any time during the last week of cycle 1. Should be obtained on the next consecutive cycle after initial documentation of either a PR or CR. Subsequent scans may restart 2 cycles after the confirmatory scan. Please note that for solid tumor patients, if the institutional investigator determines that the patient has progressed based on clinical or laboratory evidence, he/she may opt not to confirm this finding radiographically.
- k. Pregnancy test: Women of childbearing potential require a negative pregnancy test prior to starting treatment; sexually active patients must use an acceptable method of birth control. Abstinence is an acceptable methods of birth control. All women of childbearing potential must have a pregnancy test done every cycle prior to initiation of a new cycle.
- l. Medication Diary
- m. Pathology & Genomics Report: #Indicate a qualifying molecular aberration to enroll on study. Must be submitted via upload to MediData/RAVE. Details of genomic studies noted in [Section 4.1.4.3](#).
- n. Knee X-Ray: % Knee X-Ray should only be obtained in patients without epiphyseal closure at the time of enrollment, prior to start of therapy. If the baseline tibial radiographs demonstrate open growth plates (epiphysis) then knee X-rays for tibial growth plate assessment will be obtained after cycle 1, every 3 cycles thereafter and at the end of study treatment. The end of study treatment observation is not required, if already obtained within the final month of therapy. Reference [Section 8.7](#) for further instruction on monitoring for growth plate toxicity.
- o. Pharmacokinetics (required): &See [Section 8.5.2](#) for timing of PK studies
- p. Pharmacokinetics (optional): 'See [Section 8.3.5](#) for timing of optional PK studies
- q. Correlative Studies (required): \$See [Section 8.6](#) for details
- r. Correlative Studies (optional): @See [Section 8.3](#) for details

5.7: THERAPY DELIVERY MAPS (TDMS) FOR CYCLES 2 +

Page 1 or 2

Therapy Delivery Map – Cycle 2 +

This Therapy Delivery Map (TDM) relates to Cycle 2+. This TDM can be used for any dose level of BAY 1895344 (elimusertib). Please record the dose level in the chart below. Treatment may continue in the absence of unacceptable toxicity. Use a copy of this page once for Cycle 2 +.

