This form is to be completed and uploaded into RAVE at the end of every cycle.

Criteria to start this cycle are listed in [Section 5.2](#). Extensive details are in [Section 5.0](#) and [Section 9.0](#).

This TDM is on 2 pages.

DRUG	ROUTE	DOSAGE	DAYS	IMPORTANT NOTES
BAY 1895344 (elimusertib) IND# [REDACTED]	Oral (Tablet)	mg/m ² /dose BID Dose level 1 max dose = 40 mg BID Dose level -1 max dose = 30 mg BID Part B patients ≥ 18 years old: 40 mg BID	1-3 8-10 15-17 22-24	On days that BAY 1895344 (elimusertib) is due to be given, it should be administered twice daily, preferably at the same time of day each day. Take BAY 1895344 (elimusertib) one (1) hour before or two (2) hours after a meal with plenty of water.

Assigned Dose Level Ht cm Wt kg BSA m² Age ≥ 18 years yes no

Date Due	Date Given	Day	BAY 1895344 (elimusertib) Nomogram Dose mg qAM. mg qPM	Studies
Enter actual dose administered below				
		1	mg mg	a-d, e*, f, g, i, j&
		2	mg mg	
		3	mg mg	
		4		
		5		
		6		
		7		
		8	mg mg	
		9	mg mg	
		10	mg mg	
		11		
		12		
		13		
		14		
		15	mg mg	e*
		16	mg mg	
		17	mg mg	
		18		
		19		
		20		
		21		
		22	mg mg	
		23	mg mg	
		24	mg mg	a-d, h^, j&, k!, l#
		25		
		26		
		27		
		28		

* Please refer to [Section 8.1](#) for the specific timing of these observations.

Cycle 2 +

Required Observations in Cycle 2 +

Page 2 or 2

- a. History
- b. Physical Exam
- c. Height, Weight, BSA
- d. Vital Signs
- e. CBC, differential, platelets: * **Must be obtained within 72 hours of the start of each cycle and on day 15 of all subsequent cycles.** If patients develops Grade 4 neutropenia or Grade 3 or 4 thrombocytopenia, CBC/differential/platelets should be checked at least twice weekly (every 3-4 days) until recovery to Grade 3 neutropenia, Grade 2 thrombocytopenia or until the criteria for dose limiting toxicity are met. For patients who experience hematological dose limiting toxicity, CBCs should be checked at least weekly until recovery of ANC and platelet count to eligibility criteria. Patients who have dose adjustment due to hematologic toxicity attributable to BAY 1895344 (elimusertib), are required to have CBCs once weekly to confirm the safety of this adjusted dose during the cycle. Please see [Section 6.1](#) for details.
- f. SGPT (ALT), Albumin, Bilirubin
- g. Electrolytes including serum creatinine, calcium (Ca⁺⁺), phosphorus (PO₄), magnesium (Mg⁺⁺)

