8.0 EVALUATIONS/MATERIAL AND DATA TO BE ACCESSIONED

Timing of protocol therapy administration, response assessment studies, and surgical interventions are based on schedules derived from the experimental design or on established standards of care. Minor unavoidable departures (up to 72 hours) from protocol directed therapy and/or disease evaluations (and up to 1 week for surgery) for valid clinical, patient and family logistical, or facility, procedure and/or anesthesia scheduling issues are acceptable (except where explicitly prohibited within the protocol)

8.1 Required Clinical, Laboratory and Disease Evaluation (See [Section 4.0](#) for eligibility criteria to start therapy)

STUDIES TO BE OBTAINED	Pre-Study	During Cycle 1	Prior to and During Cycles 2 + [^]	End of Study Treatment
History	X	X ⁶	X	X
Physical Exam	X	X ⁶	X	X
Performance Status	X			
Height, weight, BSA	X	X ⁶	X	X
Vital Signs	X	Weekly	X	X
CBC, differential, platelets ¹	X ⁷	Weekly	X ⁶	As clinically indicated
SGPT (ALT), Albumin, Bilirubin	X ⁷	X	X ⁶	As clinically indicated
Electrolytes including serum creatinine, Ca ⁺⁺ , PO ₄ , Mg ⁺⁺	X ⁷	X	X ⁶	As clinically indicated
Creatinine Clearance or GFR	X			
Pregnancy Test ²	X			
Tumor Disease Evaluation ³	X	Last week of Cycle 1	Last week of cycles 2, 4, and 6 then q 3 cycles ³	X
Tibial Radiographs (Knee X-Ray) ⁴	X		X	X
Medication Diary see Appendix VI		Weekly	X	
Pathology & Genomics Report ⁵	X			
Pharmacokinetics (Required) See Section 8.5		X		
Pharmacokinetics (Optional) See Section 8.3.5		X		
Archival Tumor Tissue for immunohistochemistry: ATM. (Required) See Section 8.6 .	X			
Tumor Tissue for Whole Genome Sequencing (Optional) Section 8.3.1	X			X
Archival Tumor Tissue for Immunohistochemistry: PGBD5 and R-Loops (Optional) Section 8.3.2	X			
Tumor Tissue for Immunohistochemistry pH2AX, pKAP1 and pATR (Optional) Section 8.3.3	X			X
Blood for ctDNA for ALT (Optional) Section 8.3.4	X			
Archival Tumor Tissue for Biobanking (Optional) Section 8.3.5	X			

[^] Studies may be obtained within 72 hours prior to the start of the subsequent cycle.

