¹ If patients develop Grade 4 neutropenia or Grade 3 or 4 thrombocytopenia, CBC/differential/platelets should be checked twice per week (every 3 to 4 days) until recovery to Grade 3 neutropenia, Grade 2 thrombocytopenia, or until the criteria for dose limiting toxicity are met. For patients with hematological dose limiting toxicity, CBCs should be checked at least weekly until recovery to eligibility criteria. Please see [Section 5.2.1](#) for details.

THIS PROTOCOL IS FOR RESEARCH PURPOSES ONLY, SEE PAGE 1 FOR USAGE POLICY

- ² Women of childbearing potential require a negative pregnancy test prior to starting treatment; See [Section 4.2.1](#)
- ³ Tumor Disease Evaluation [^]should be obtained on the next consecutive cycle after initial documentation of either a PR or CR. Subsequent scans may restart 2 cycles after the confirmatory scan. Please note that for solid tumor patients, if the institutional investigator determines that the patient has progressed based on clinical or laboratory evidence, he/she may opt not to confirm this finding radiographically.
- ⁴ Tibial Radiographs should only be obtained in patients without epiphyseal closure at the time of enrollment, prior to start of therapy and if baseline tibial radiographs are open then another will be obtained after cycle 1, every 3 cycles thereafter and at the end of study treatment. The end of study treatment observation is not required, if already obtained within the final month of therapy. Reference [Section 8.7](#) for further instruction on monitoring for growth plate toxicity.
- ⁵ Tumor pathology and genomics report indicating a qualifying molecular aberration to enroll on study must be submitted via upload to MediData/RAVE. Details of genomic studies noted in [Section 4.1.3](#).

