- ⁶ Must be obtained within 72 hours of the start of each cycle and on day 15 of all subsequent cycles. If patients develop Grade 4 neutropenia or Grade 3 or 4 thrombocytopenia, CBC/differential/platelets should be checked at least twice weekly (every 3-4 days) until recovery to Grade 3 neutropenia, Grade 2 thrombocytopenia or until the criteria for dose limiting toxicity are met. For patients who experience hematological dose limiting toxicity, CBCs should be checked at least weekly until recovery of ANC and platelet count to eligibility criteria. Patients who have a dose adjustment due to hematologic toxicity attributable to BAY 1895344 (elimusertib), are required to have CBCs checked once weekly to confirm the safety of this adjusted dose during the cycle. Please see [Section 6.1](#) for details.
- ⁷ If greater than 7 days from pre study labs, please collect CBC, differential, platelets, bilirubin, albumin and serum creatinine within 48 hours prior to cycle 1, dose 1. These labs must still meet eligibility to receive dose 1 (as per [Section 4.0](#)).

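### The protocol contradicts itself on repeat pregnancy testing: the Cycle 1 map requires a test before every cycle, but the pages that govern later cycles schedule none

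*Combined protocol and SAP*

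**What the plan says.** Pregnancy testing appears in these places in the current text:

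- **Section 4.2.1** (exclusion criteria): "Pregnancy tests must be obtained in girls who are post-menarchal". No repeat interval is given.
- **Section 5.6, Cycle 1 map, observation k**: "All women of childbearing potential must have a pregnancy test done every cycle prior to initiation of a new cycle". The map is a single-use form for the first cycle, and k appears in its day grid only in the PRE row.
- **Section 5.7, Cycle 2+ map**: neither the day grid nor the list headed "Required Observations in Cycle 2" (items a to l) contains a pregnancy test. Letter k on this map is an optional tumor tissue sample.
- **Section 8.1 table**: the row "Pregnancy Test" has one mark, under Pre-Study. The cells for Cycle 1, Cycles 2+ and end of treatment are empty.
- **Section 8.1, footnote 2**: "Women of childbearing potential require a negative pregnancy test prior to starting treatment", with a reference back to Section 4.2.1.
- **Section 5.2**: among the conditions for starting a further cycle is that "all pre-cycle studies required per" Section 8.1 meet the eligibility criteria.

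On the laboratory recheck before the first dose, Section 4.0 lists "CBC with differential, bilirubin, ALT (SGPT), albumin and serum creatinine". Section 8.1 footnote 7 says "please collect CBC, differential, platelets, bilirubin, albumin and serum creatinine within 48 hours prior to cycle 1, dose 1", which leaves out ALT.

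**The concern.** The only statement of the per-cycle rule sits on a form that is put away after Cycle 1. The pages that staff use from Cycle 2 onward (the Cycle 2+ map, the Section 8.1 schedule and the Section 5.2 cycle-start rule) do not carry it.

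The protocol's own provisions show why the schedule should be unambiguous. Patients of reproductive potential must agree to contraception (Section 4.2.1, which also accepts abstinence). Pregnancy is a reason for removal from protocol therapy (Section 10.1). It is reported in an expedited manner because the fetus may be exposed to a teratogenic agent (Section 13.4.5.1). Part B enrolls patients up to age 30 in two cohorts and up to 21 in the third (Section 4.1.2).

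An omission might not be noticed quickly. The central monitoring plan in Appendix II does not list pregnancy testing, and the on-site source verification in Section 14.4 is retrospective and annual.

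**Working it through.** The plan gives no statistical figure on this point. The check is a comparison of passages plus one count.

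**Step 1. The schedules side by side.**

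| Place | Before Cycle 1 | Before each of Cycles 2 to 26 |
|---|---|---|
| 5.6 observation k, text | required | required |
| 5.6 day grid | k in PRE row | outside the scope of this map |
| 5.7 grid and list | outside the scope of this map | no entry |
| 8.1 table | marked | cell empty |
| 8.1 footnote 2 | required | not mentioned |
| 4.2.1 | required at entry | not mentioned |

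All sources that address the baseline test agree on it. For later cycles, one sentence requires the test and no schedule or later-cycle form lists it.

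**Step 2. Does the cycle-start rule close the gap?** Section 5.2 requires the pre-cycle studies listed in Section 8.1 to meet eligibility. Pregnancy is an exclusion under Section 4.2.1, but Section 8.1 lists no pregnancy test after pre-study, so Section 5.2 has no result to check. It leads the site back to the page that omits the test.

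**Step 3. Count.** Let n be the number of cycles a patient of childbearing potential starts.

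- Under observation k: n tests, one before each cycle.
- Under the 8.1 table with the Cycle 2+ map: 1 test.
- Difference: n − 1.

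The maximum is 26 cycles (Section 5.1), which gives 26 − 1 = 25. The documents state no expected duration of treatment, so only a range can be given: n = 1 gives 0; n = 6, the response-evaluation period in Section 12.2.1.2, gives 5; n = 26 gives 25.

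**Step 4. The ALT lists.** Both describe a recheck within 48 hours before therapy, and they differ by one analyte, ALT. Three points limit the consequence:

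- The footnote 7 marker sits on the pre-study cell of the table row that contains ALT.
- Footnote 7 refers to Section 4.0, which names ALT in the recheck.
- Section 4.0 also limits the age of eligibility laboratory values to seven days at the start of therapy, and ALT is an eligibility value under Section 4.1.11.3.

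**The case against.** The strongest reply is that this is an omission with a clear answer. Observation k is phrased as an obligation covering every cycle, and no passage says that testing stops after baseline. Footnote 2 gives a baseline requirement without the word only, and the Cycle 2+ map is silent. A reader might infer from the mismatch that two sites could both comply with the protocol while testing differently. The documents do not support that: a site that skips the later tests departs from an explicit requirement.

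This reply corrects how the point is stated but does not remove it. The obligation appears on a form not used after Cycle 1, while the schedule table, the later-cycle map and the cycle-start rule all lead the site away from it. A site could depart from the protocol without knowing it.

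A second tempting inference is that a site relying on footnote 7 could properly give the first dose without a current ALT. That also fails. Footnote 7 cites Section 4.0, which requires the ALT recheck and the seven-day limit, and Section 10.1(g) removes patients whose repeat eligibility studies fall outside limits before Cycle 1. The Cycle 1 map also lists ALT in both the PRE and Day 1 rows, although that entry does not itself state a 48-hour check before dosing. What remains is a wording slip.

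It is also fair to say that 25 is a ceiling. Patients have recurrent or refractory disease and leave treatment at progression, so it should not be read as a typical number.

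**Conclusion.** The contradiction on repeat pregnancy testing stands. It is an internal inconsistency in the current text and does not come from the summary of changes. Its size is n − 1 tests for a patient of childbearing potential who starts n cycles, with a maximum of 25 at 26 cycles. That count assumes a site that works from Section 8.1 and the Cycle 2+ map and does not carry the Cycle 1 observation forward. How many sites would do so cannot be learned from the documents.

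The ALT difference is editorial only. Neither item bears on the dose-finding rules, the response endpoint, type I error or power. The point deserves correction because it concerns safety testing and is cheap to settle. Which schedule is right is a clinical decision and is not judged here.

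**What to change.** Reconcile Section 5.6 observation k, the Section 5.7 day grid and observation list, the Section 8.1 table row and Section 8.1 footnote 2 so that all state one pregnancy-test schedule. If the schedule includes later cycles, Section 5.2 will pick it up through its reference to Section 8.1.

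As an editorial item in the same amendment, make the recheck list in Section 8.1 footnote 7 match the one in Section 4.0. Their triggers can be aligned too: Section 4.0 also calls for a recheck when a post-enrollment value is outside limits, and footnote 7 gives only the age of the laboratory results.

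The cost is amendment wording and revised delivery maps. Any test added to a page would be routine, and no analysis or sample-size text changes.

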Therapy Delivery Map – Cycle 1

This Therapy Delivery Map (TDM) relates to Cycle 1. Cycle 1 lasts 28 days. Please record the dose level in the chart below. Treatment may continue in the absence of unacceptable toxicity. Use a copy of this page once for Cycle 1.

This form is to be completed and uploaded into RAVE at the end of every cycle.

Criteria to start this cycle are listed in [Section 5.2](#). Extensive details are in [Section 5.0](#) and [Section 9.0](#).

This TDM is on 2 pages.

DRUG	ROUTE	DOSAGE	DAYS	IMPORTANT NOTES
BAY 1895344 (elimusertib) IND# [REDACTED]	Oral (Tablet)	_____ mg/m ² /dose BID Dose level 1 max dose = 40 mg BID Dose level -1 max dose = 30 mg BID Part B patients \geq 18 years old: 40 mg BID	1-3 8-10 15-17 22-24	On days that BAY 1895344 (elimusertib) is due to be given, it should be administered twice daily preferably at the same time of day each day. Take BAY 1895344 (elimusertib) one (1) hour before or two (2) hours after a meal with plenty of water.

Assigned Dose Level Ht cm Wt kg BSA m² Age \geq 18 years yes. no

Date Due	Date Given	Day	BAY 1895344 (elimusertib) Nomogram Dose mg qAM. _____ mg qPM	Studies
Enter actual dose administered below				
		PRE	_____ mg _____ mg	a-e, f*, g-i, j^, k, m#, n%, q\$, r@
		1	_____ mg _____ mg	a, b, d, e, f*, g, h, l, o&, p!
		2	_____ mg _____ mg	
		3	_____ mg _____ mg	o&
		4		
		5		
		6		
		7		
		8	_____ mg _____ mg	e, f* 1
		9	_____ mg _____ mg	
		10	_____ mg _____ mg	o&, p!
		11		
		12		
		13		
		14		
		15	_____ mg _____ mg	e, f*, 1
		16	_____ mg _____ mg	
		17	_____ mg _____ mg	
		18		
		19		
		20		
		21		
		22	_____ mg _____ mg	e, f*, j^, 1
		23	_____ mg _____ mg	
		24	_____ mg _____ mg	
		25		
		26		
		27		
		28		

* Please refer to [Section 8.1](#) for the specific timing of these observations.

Observations in Cycle 1

- a. History
- b. Physical Exam
- c. Performance Status
- d. Height, Weight, BSA
- e. Vital Signs
- f. CBC, differential, platelets: *Once weekly. If patients develop Grade 4 neutropenia or Grade 3 or 4 thrombocytopenia, CBC/differential/platelets should be checked at least twice per week (every 3-4 days) until recovery to Grade 3 neutropenia or Grade 2 thrombocytopenia, or until the criteria for dose limiting toxicity are met. For patients who experience hematological dose limiting toxicity, CBCs should be checked at least weekly until recovery of ANC and platelet count to eligibility criteria
- g. SGPT (ALT), Albumin, Bilirubin

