- h. Tumor disease evaluation: ^**Can occur any time during the last week of cycles 2, 4 and 6 and then every 3 cycles thereafter.** Should be obtained on the next consecutive cycle after initial documentation of either a PR or CR. Subsequent scans may restart 2 cycles after the confirmatory scan. Please note that for solid tumor patients, if the institutional investigator determines that the patient has progressed based on clinical or laboratory evidence, he/she may opt not to confirm this finding radiographically.
- i. Medication Diary
- j. Knee X-Ray: & **Knee X-Ray should only be obtained in patients without epiphyseal closure at the time of enrollment, prior to start of therapy. If the baseline tibial radiographs demonstrate open growth plates (epiphysis) then knee X-rays for tibial growth plate assessment will be obtained after cycle 1, every 3 cycles thereafter and at the end of study treatment. The end of study treatment observation is not required, if already obtained within the final month of therapy.**
- k. Tumor Tissue for Immunohistochemistry pH2AX, pKAP1 and pATR (Optional): 'See [Section 8.3.3](#) for details.
- l. Tumor Tissue for Whole Genome Sequencing (Optional): #See [Section 8.3.1](#) for details.

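### A pregnancy test before every cycle is required in 5.6(k), but the 8.1 schedule, the Cycle 2+ map in 5.7 and the cycle-start rule in 5.2 do not carry it

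*Combined protocol and SAP*

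**What the plan says.** Five places in the protocol bear on pregnancy testing.

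- **5.6, Cycle 1 map, observation k.** It asks for a negative test before treatment and then adds: "All women of childbearing potential must have a pregnancy test done every cycle prior to initiation of a new cycle". The map is single-use ("Use a copy of this page once for Cycle 1"), and its studies column shows k in the PRE row only.
- **5.7, Cycle 2+ map** ("This Therapy Delivery Map (TDM) relates to Cycle 2" and later cycles). It lists observations a to l. None is a pregnancy test. The letter k is reused there for "Tumor Tissue for Immunohistochemistry pH2AX, pKAP1 and pATR (Optional").
- **8.1, required evaluations.** The row "Pregnancy Test" has a single mark, under Pre-Study. Footnote 2 asks for a negative result before treatment begins, refers to 4.2.1, and sets no repeat.
- **5.2, starting later cycles.** One condition is that "all pre-cycle studies required per [Section 8.1](#) meet eligibility criteria", as Section 4.0 defines them.
- **4.2.1, exclusion for pregnancy.** "Pregnancy tests must be obtained in girls who are post-menarchal". No repeat interval is given.

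**The concern.** The only per-cycle instruction sits on a page that is used once, before any later cycle is due. The pages a site works from in Cycles 2 to 26 do not prompt the test, and the rule that releases each new cycle does not depend on it. The sections therefore give different answers to one question: is a test required before Cycle 2 and each later cycle?

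What is at stake is participant and fetal safety. Section 13.4.5.1 warns that a fetus could be exposed to drugs with possible teratogenic effect, and 10.1(i) takes a pregnant patient off therapy. That removal rule works only if the pregnancy is found. There is also a compliance problem: a missing test from Cycle 2 on is a deviation under 5.6(k) but not under 8.1, so a site and an auditor can disagree, each with text in support.

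**Working it through.** The plan states no figure to reproduce. The check is a comparison of the sections, followed by a count.

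**Step 1. What each section requires of a woman of childbearing potential**

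| Section | Before Cycle 1 | Before each of Cycles 2–26 |
|---|---|---|
| 5.6(k), text | Yes | Yes |
| 5.6, map grid | Yes (PRE row) | Not shown; the map covers Cycle 1 only |
| 5.7, Day 1 studies (a–d, e, f, g, i, j) | Not applicable | No |
| 8.1 table and footnote 2 | Yes | No |
| 5.2, start rule | Not applicable | Only what 8.1 requires, so no |
| 4.2.1 | Yes (entry) | Silent |

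The reading of 8.1 does not depend on how the table was extracted from the PDF, because footnote 2 gives the same timing in prose.

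The repeat knee X-ray is a useful comparison. It appears in 5.6(n), 5.7(j), the Cycles 2+ column of 8.1, footnote 4 and 8.7. The repeat pregnancy test appears in none of the Cycle 2+ texts.

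**Step 2. Tests per patient**

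Inputs: at most 26 cycles of 28 days (5.1). The next cycle may start up to 14 days late (5.5.2 and 6.1.3).

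- Tests under 5.6(k) for a patient who starts n cycles: n
- Tests under 8.1 and 5.7: 1
- Difference: n − 1

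So n = 2 gives 1, n = 6 gives 5, and n = 26 gives 25.

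**Step 3. Time without a scheduled test**

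- Under 8.1: nominal treatment after the only test is up to 26 × 28 = 728 days.
- Under 5.6(k): about 28 days between tests, or 28 + 14 = 42 with the longest allowed delay.

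**Step 4. Trial total, on assumptions**

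Section 11.10 plans 34 + 7 = 41 female patients among 90. The documents do not say how many are of childbearing potential. The shares below are assumptions, and so is the number of cycles started, taken as equal for all patients.

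| Assumed share | Patients | 2 cycles (×1) | 6 cycles (×5) | 26 cycles (×25) |
|---|---|---|---|---|
| 25% | 10 | 10 | 50 | 250 |
| 50% | 20 | 20 | 100 | 500 |
| 100% | 41 | 41 | 205 | 1,025 |

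Entries are tests that 5.6(k) requires and that neither 8.1 nor 5.7 schedules.

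**The case against.** The strongest reply is that this is an omission and not a true conflict. No section says the test is unnecessary after baseline. A test before treatment and a test before each later cycle are compatible, 5.6(k) states both, and a site that tests every cycle satisfies every section. An explicit requirement is not cancelled by an empty table cell. The 5.7 map also refers readers to Section 5.0 for details, and 5.6(k) lies within it. On this view 5.2 adds nothing of its own, since it only imports what 8.1 lists.

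Much of that is fair. Testing every cycle is the safe reading, and the gaps in 5.2 and 8.1 have one source. But the reply shows only that a careful reader can comply. It does not make the Cycle 2+ checklist or the start rule ask for the test, and a general pointer to the whole of Section 5.0 is a poor substitute for a line in the checklist. Nor does the reference in 5.2 to Section 4.0 eligibility help, because a test that 8.1 does not require yields no result to judge.

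Two further objections concern size and visibility. The upper figures are ceilings: eligibility starts at 12 months of age, so not all 41 female patients will be post-menarchal, and few patients with relapsed or refractory disease may be expected to reach 26 cycles. That stands. The separate case report form packet and the consent forms, which could not be examined, might carry the per-cycle test. That also stands, but it would not correct the protocol text.

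**Conclusion.** The concern holds, at minor severity. The every-cycle test in 5.6(k) is missing from each section that governs Cycles 2 to 26, and following 5.2, 5.7 and 8.1 exactly leads to a breach of 5.6(k).

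The firm measure of size is n − 1 unscheduled tests per woman of childbearing potential who starts n cycles, up to 25. The trial-wide range of 10 to 1,025 rests on assumed shares of 25% to 100% and on 2 to 26 cycles each. Its upper end is a bound and not an expectation.

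Detection of pregnancy is weakened, not absent: the two-method contraception rule in 4.2.1 and the history and physical examination each cycle still apply. The effect is on participant and fetal safety and on audit consistency. The statistical design and analysis are untouched.

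**What to change.** Carry the 5.6(k) requirement into the schedules used from Cycle 2 on:

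- In the 8.1 table, mark the pregnancy test under the Cycles 2+ column.
- Extend footnote 2 so that the test is due before treatment starts and again within 72 hours before each new cycle. This matches the window 8.1 already allows for pre-cycle studies.
- Add the same observation to Day 1 of the Cycle 2+ map in 5.7.

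Section 5.2 then needs no edit, because its reference to 8.1 brings the test into the start rule.

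The cost is one table row, one footnote and one map line. Each woman of childbearing potential has one test per cycle, which 5.6(k) already demands, at a visit where CBC, ALT and electrolytes are already required. No visit is added and the analysis does not change.
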